3.3. Safety Analysis Sets

The double-blind safety analysis set will include all randomized patients who receive at least 1 dose of IMP during the double-blind treatment period. The open-label safety analysis set will include all patients who receive at least 1 dose of IMP during the open-label treatment period.

In the safety analysis sets, treatment will be assigned based on the treatment patients actually received, regardless of the treatment to which they were randomized.

3.4. Per-Protocol Analysis Set

The per-protocol (PP) analysis set is a subset of the double-blind mITT analysis set including only patients without important deviations such as important inclusion/exclusion criteria deviations or any important deviations or omissions of the IMP administration. In the PP analysis set, treatment will be assigned based on the treatment patients actually received, regardless of the treatment to which they were randomized. Patients with less than 75% diary compliance during the double-blind treatment period will be excluded from the PP analysis set. Patients who received study drug different from the study drug they were randomized to will be excluded from the PP analysis set. A blinded data review meeting will be conducted prior to the first interim database lock in order to determine the exclusion of the patients from the PP analysis set.

4. GENERAL ISSUES FOR DATA ANALYSIS

4.1. General

Descriptive statistics for continuous variables include n, mean, standard deviation (SD), standard error (SE), median, minimum, and maximum. Descriptive statistics for categorical variables include patient counts and percentages; missing categories will be displayed as appropriate.

Data collected at the follow-up visit (visit 9) will be listed only.

4.2. Specification of Baseline Values

Patients will complete electronic headache diary entries daily for the 28-day run-in period, subjectively rating their headaches as mild, moderate, or severe and enter headache information about the previous day into the electronic headache diary device. If the run-in period is greater or less than 28 days, the baseline values for calculating the change from baseline of the monthly values of the efficacy variables will be prorated to **28** days.

The efficacy baseline values during the 28-day run-in period derived from the electronic headache diary device include

- total number of migraine days
- total number of days of use of any acute headache medications (as collected in the daily diary ie. in addition to randomized treatment)
- total number of headache days of at least moderate severity
- total number of headache days of any severity
- total number of headache hours of at least moderate severity
- total number of days with nausea or vomiting
- total number of days with photophobia and phonophobia
- total number of days of use of migraine-specific acute headache medications (triptans and ergot compounds)

Otherwise baseline value will be the last non-missing value prior to the 1st dose of study drug, unless otherwise noted.

4.3. Handling Withdrawals and Missing Data

If a patient has ≥ 10 days of electronic headache diary data after the 1st dose of the study drug, his/her monthly average number of days/hours of efficacy variables *during the 12-week double blind period* will be prorated to **28** days. Similarly, if a patient has ≥ 10 days of electronic headache diary data after the 4th dose of the study drug, his/her monthly average number of days/hours of efficacy variables *during the 12-week open label period* will be prorated to **28** days.

Patients who have <10 days of electronic headache diary data for the primary endpoint during the double blind period will be excluded from the double blind mITT analysis set. Patients who

have <10 days of electronic headache diary data during the open label period will be excluded from the open label mITT analysis set.

A patient's monthly number of days of efficacy variables *during the 4-week period* after each dose of study drug will be calculated. If a patient has missing diary days in a month, the following method will be used to handle the missing data.

- If the patient has 10 or more days of electronic headache diary data for a month, the monthly number of days/hours of efficacy variables will be prorated to **28** days for that month.
- If the patient has less than 10 days of electronic headache diary data for a month, the monthly number of days/hours of efficacy variables will be considered as missing.

A sensitivity analysis will be performed to assess the primary estimand using mixed-effects model for repeated measures (MMRM) as a different missing data handling approach. The methods will be described in detail in Section 6.2.3.1.

Multiple imputation (MI) method will be applied on the primary variable as sensitivity analyses. The methods will be described in detail in Section 6.2.3.2.

4.4. Study Days and Visits

Study days will be numbered relative to the 1st day of study drug administration. The start of treatment (visit 2 or day 1) is defined as the date on which a patient takes the 1st dose of study drug, as recorded on the study drug administration case report form (CRF). Days will be numbered relative to study drug start (ie, ..., -2, -1, 1, 2, ...; with day 1 being the start of study drug and day -1 being the day before the start of study drug).

The 4-week (28-day) visit windows for the electronic headache diary device efficacy endpoints will be determined based on the actual dosing day. The run-in phase is defined as day -28 to -1 before the 1st injection on day 1. The 4-week period after the 1st dose of IMP is from the beginning of the 1st injection of study drug to just before the 2nd dose at visit 3/day 28. The 12-week double-blind treatment period is from the beginning of the 1st injection of study drug to just before the 2nd dose at visit 3/day 28. The 12-week double-blind treatment period is from the beginning of the 1st injection of study drug to just before the 7th dose at visit 8/day 168 or the end of treatment visit. The follow-up period lasting 3 months after the last dose of IMP is from visit 8/day 169 to visit 9/day 224 or the end of study visit. Throughout this document, all by month efficacy summaries for the headache data will refer to these visit windows. If the Month 2, 3, 4, 5, 6 or 7 dosing day is missed, then the dosing day is considered to be previous dosing day +28 days. For all by-visit summaries, if there are multiple assessments at a postbaseline visit then the last non-missing assessment at that visit will be used for the summary. This includes assessments at the scheduled and unscheduled visits.

Unless otherwise stated, Last Assessment for summaries is the last observed postbaseline data. For patients who withdraw from the study, data at the early termination visit will be excluded from the by-visit summaries but will be included in the Last Assessment summaries.

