Treatment (active or placebo) will be administered at visit 2, visit 3, and visit 4. Active treatment will be administered to all patients at visit 5, visit 6, and visit 7. Final treatment evaluation will be performed at visit 8 (EOT), approximately 4 weeks after administration of the last dose of study drug.

The IMP is defined as the test IMP (fremanezumab) and matching placebo IMP. Fremanezumab and placebo are characterized in [Table 2](#).

Table 2: Investigational Medicinal Products Used in the Study

| IMP name | Fremanezumab, a fully humanized IgG2Δa/kappa mAb | Placebo |
|--|---|--|
| Trade name and INN, if applicable, or company-assigned number | AJOVY Fremanezumab TEV-48125 | Placebo |
| Formulation | Prefilled syringes containing 150 mg/mL of active ingredient: fremanezumab Inactive ingredients include L-histidine, L-histidine hydrochloride monohydrate, sucrose, polysorbate-80, disodium EDTA dihydrate, and water for injection | Prefilled syringes containing 1.5 mL of the same inactive vehicle and excipients that are in the active injections Inactive ingredients include L-histidine, L-histidine hydrochloride monohydrate, sucrose, polysorbate-80, disodium EDTA dihydrate, and water for injection |
| Unit dose strength(s)/ Dosage level(s) | 225 mg | None |
| Route of administration | sc injection | sc injection |
| Dosing instructions | Quarterly: fremanezumab 675 mg as 3 injections (225 mg/1.5 mL) at visit 2; 1 placebo (1.5 mL) injection at visits 3 and 4 Monthly: fremanezumab 225 mg as 1 injection (225 mg/1.5 mL) and 2 placebo (1.5 mL) injections at visit 2; fremanezumab 225 mg as 1 injection (225 mg/1.5 mL) at visits 3 and 4 | 3 placebo (1.5 mL) injections at visit 2; 1 placebo (1.5 mL) injection at visits 3 and 4 |
| Packaging | A uniquely numbered kit containing 1 prefilled syringe stored (refrigerated at 2°C to 8°C) on site | A uniquely numbered kit containing 1 prefilled syringe stored (refrigerated at 2°C to 8°C) on site |
| Manufacturer | Drug substance: ██████████ ████████████████████ ██████████████████ ██████████████████ Drug product: ████████████████████ ██████████ ██████████████████ ██████████████████ | ██ ██████████ ██████████████████ ██████████████████ ██████████ |

EDTA=ethylenediaminetetraacetic acid; IgG2Δa=immunoglobulin G2Δa; IMP=investigational medicinal product; INN=international nonproprietary name; mAb=monoclonal antibody; sc=subcutaneous.

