^b The EOS is defined as the last visit of the last patient. Each patient attends his/her follow-up visit approximately 3 months after the last dose of IMP (approximately 2 months after the EOT/ET visit [visit 8]).

^c In case of an emergency situation (eg, pandemic or potential pandemic), visit windows for post baseline visits may be extended to 14 calendar days, except for visit 2. The window for visit 2 may only be extended to 7 calendar days in case of an emergency situation (eg, pandemic or potential pandemic). In case of an out-of-window visit, the date of the next visit will be calculated based on the actual date of the last administration of study drug.

^d Collection of prior medications is limited to those medications administered within 6 months before IMP administration (visit 2) and preventive medications taken within 10 years.

^e At visits where IMP is administered, clinical laboratory tests should be performed predose.

^f To be performed at visit 9 (follow-up) if assessment at visit 8 (EOT/ET) shows abnormality.

^g Blood samples for plasma drug concentration determination will be collected prior to dosing (as appropriate). Patients will be asked to return to the study center after visit 2, visit 3, or visit 4 for 2 additional blood sampling visits to measure plasma fremanezumab concentration (one being 3 to 10 days after either visit 2, visit 3, or visit 4 and the other being 15 to 20 days after either visit 2, visit 3, or visit 4). If 2 additional visits are not possible for the patient, then the patient must return for only 1 additional pharmacokinetic blood sampling at either of the aforementioned time points. When patients return to the study center for additional blood sampling, then inquiries about adverse events and concomitant medications will be performed.

^h Blood samples for serum ADA assessment will be collected prior to dosing (as appropriate).

ⁱ Height will be measured only at the screening visit.

^j A single ECG will be performed predose. The ECG should be performed after the patient has been supine for at least 5 minutes. If results are abnormal, the ECG will be repeated 1 time.

Clinical Study Protocol with Amendment 02 with Revision 01

^k Before pulse and blood pressure are measured, the patient must be in a supine or semi-erect/seated position and resting for at least 5 minutes. The same position and arm should be used each time vital signs are measured for a given patient.

^l Procedures for unscheduled visits.

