5. TREATMENTS

5.1. Investigational Medicinal Products Used in the Study

Treatment (active or placebo) will be administered at visit 2, visit 3, and visit 4. Active treatment will be administered to all patients at visit 5, visit 6, and visit 7. Final treatment evaluation will be performed at visit 8 (EOT), approximately 4 weeks after administration of the last dose of study drug.

IMP is defined as the test IMP (fremanezumab) and matching placebo IMP. A summary of IMPs is presented in [Table 4](#). Additional details may be found in the IB for fremanezumab.

Table 4: Investigational Medicinal Products Used in the Study

| IMP name | Fremanezumab, a fully humanized IgG2Aa/kappa mAb | Placebo |
|--|---|--|
| Trade name and INN, if applicable, or company- assigned number | AJOVY Fremanezumab TEV-48125 | Placebo |
| Formulation | Prefilled syringes containing 150 mg/mL of active ingredient: fremanezumab Inactive ingredients include L-histidine, L-histidine hydrochloride monohydrate, sucrose, polysorbate-80, disodium EDTA dihydrate, and water for injection | Prefilled syringes containing 1.5 mL of the same inactive vehicle and excipients that are in the active injections Inactive ingredients include L-histidine, L-histidine hydrochloride monohydrate, sucrose, polysorbate-80, disodium EDTA dihydrate, and water for injection |
| Unit dose strength(s)/ Dosage level(s) | 225 mg | None |
| Route of administration | sc injection | sc injection |
| Dosing instructions | Quarterly: fremanezumab 675 mg as 3 injections (225 mg/1.5 mL) at visit 2; 1 placebo (1.5 mL) injection at visits 3 and 4 Monthly: fremanezumab 225 mg as 1 injection (225 mg/1.5 mL) and 2 placebo (1.5 mL) injections at visit 2; fremanezumab 225 mg as 1 injection (225 mg/1.5 mL) at visits 3 and 4 | 3 placebo (1.5 mL) injections at visit 2; 1 placebo (1.5 mL) injection at visits 3 and 4 |
| Packaging | A uniquely numbered kit containing 1 prefilled syringe stored (refrigerated at 2°C to 8°C) on site | A uniquely numbered kit containing 1 prefilled syringe stored (refrigerated at 2°C to 8°C) on site |
| Manufacturer | Drug substance: ██████████ ████████████████████ ██████████████████ ██████████████ Drug product: ██ ██████████████ ██████████████████ ██████████ | ██ ██████████ ██████████████████ ██████████████████ ██████████ |

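### SAP 4.4 should name the 4th dose (visit 5) as the end of the double-blind diary window, correct its reference to a seventh dose, and cap the windows when a dose is late as well as when it is missed

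*SAP*

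**What the plan says.** SAP 4.4 ties the diary windows to dosing: "The 4-week (28-day) visit windows for the electronic headache diary device efficacy endpoints will be determined based on the actual dosing day". The 4-week period after the first dose ends "just before the 2nd dose at visit 3/day 28". In the supplied text the 12-week double-blind period is then given that same end. It is defined again straight afterwards as running "to just before the 7th dose at visit 8/day 168", or to the end-of-treatment visit. The next sentence is about follow-up; no sentence gives an end at visit 5 or an open-label window.

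For a dose that is not given, in any of months 2 to 7, the rule is that if the "dosing day is missed, then the dosing day is considered to be previous dosing day +28 days". Nothing is said about a dose that is given late.

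Protocol 5.1 states: "Treatment (active or placebo) will be administered at visit 2, visit 3, and visit 4". It continues: "Active treatment will be administered to all patients at visit 5, visit 6, and visit 7". Visit 8 is the end-of-treatment visit, with no administration. Protocol Table 3 schedules visit 3 on day 29 ±3, visit 4 on day 57 ±3 and visit 5 on day 85 ±5. Under footnote c, in an emergency, "visit windows for post baseline visits may be extended to 14 calendar days, except for visit 2", and after an out-of-window visit the next date is recalculated from the last administration.

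SAP 6.1 divides the days with the event by the diary days recorded in the window and multiplies by 28. The SAP introduction says that the SAP prevails where it differs from the protocol.

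**The concern.** Section 4.4 decides which diary days enter formulas (1) and (2) of SAP 6.1, and so the primary endpoint and all four secondary efficacy endpoints. The rule should pick out 84 days for the 12-week values and 28 days for the 4-week value without further interpretation. As supplied it falls short in two ways.

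First, neither of the two ends printed for the double-blind period gives 12 weeks, and one of them names a dose that the protocol does not give.

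Second, a missed dose closes a month at 28 days, while a late dose leaves it open until the dose is given. Two patients with similar delays can therefore contribute windows of different length, with no stated reason.

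The first interim lock unblinds the study (SAP 2.5.1). A window rule settled after that point would be a choice about the primary endpoint made with treatment codes available.

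**Working it through.** **1. The plan's own schedule.** Doses every 28 days from day 1 fall on days 1, 29, 57, 85, 113 and 141, which are visits 2 to 7 in Protocol Table 3: six doses. The next 28-day step is day 169, visit 8, when no dose is given. The last day before visit 3 is day 28, before visit 5 it is day 84, and before visit 8 it is day 168. So the two day numbers in SAP 4.4 are right for the visits that they name.

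**2. The printed double-blind ends.**
- Visit 3/day 28: 28/7 = 4 weeks.
- Visit 8/day 168: 168/7 = 24 weeks.
- Required: 84/7 = 12 weeks, the day before the 4th dose at visit 5. This is not stated in 4.4 as supplied.

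Day 168 is where the open-label period would end: days 85 to 168 are 84 days. That fits an open-label sentence whose opening was lost. It does not explain the seventh dose, which the missed-dose rule echoes by listing a month 7 dosing day.

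**3. The boundary elsewhere in the SAP.** Section 2.2 starts open label at week 12. Sections 4.3 and 6.1 start the 12-week open-label period after the 4th dose. Section 2.1 ties the first lock to visit 5. Section 6.2.1 defines the primary variable over 12 weeks. All agree with days 1 to 84.

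**4. Late against missed doses.** Window length is the day of the next dose minus 1, counting from day 1. Footnote c is read as allowing a visit up to 14 days late.

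| Situation | Next dose | Window |
|---|---|---|
| Visit 3 dose missed | set to day 29 | 28 days |
| Visit 3 at +3 (routine) | day 32 | 31 days |
| Visit 3 at +14 (emergency) | day 43 | 42 days |
| Visit 5 at +5 (routine) | day 90 | 89 days |
| Visit 5 at +14 (emergency) | day 99 | 98 days |

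The extreme case, with visits 3, 4 and 5 each 14 days late and each date recalculated, is 3 × (28 + 14) = 126 days.

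**5. What proration does.** Suppose a patient has 8 migraine days per 28 inside the intended window, a complete diary, and r per 28 in e extra days. The rates are illustrative; the documents give none.

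- 4-week value: (8 + e × r/28) / (28 + e) × 28
  - e = 3: r = 6 gives 7.81; r = 10 gives 8.19
  - e = 14: r = 6 gives (8 + 3)/42 × 28 = 7.33; r = 10 gives (8 + 5)/42 × 28 = 8.67
- 12-week value: (24 + e × r/28) / (84 + e) × 28
  - e = 5: r = 6 gives 7.89; r = 10 gives 8.11
  - e = 14: r = 6 gives (24 + 3)/98 × 28 = 7.71; r = 10 gives (24 + 5)/98 × 28 = 8.29

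With r = 8 every value stays at 8.00. Proration removes the effect of length, but not that of days which differ from those in the endpoint's definition.

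**The case against.** The strongest reply is that the double-blind wording is damaged text rather than a faulty plan. A long string repeats word for word, and the ending at visit 8 sits where an open-label definition would be expected. Words lost in reading a PDF are not missing from the plan. This stands: the absence of a visit 5 end should be checked against the source before it is treated as a gap.

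A reader might infer that the primary endpoint would be computed over 4 or 24 weeks. Over 24 weeks, placebo patients would contribute 12 weeks on fremanezumab. With the 1.6-day difference that appears only in the protocol's amendment log, and no difference in open label, the contrast would halve to 0.8 days. The documents do not support this. The SAP sections in step 3 fix the boundary. The first analysis uses double-blind data and follows the last patient's visit 5, when the last patients have no diary to day 168.

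It can also be said that the term 4-week (28-day) window already implies a cap, that proration protects the value, that routine tolerance is only 3 or 5 days, and that 14 days applies only in an emergency. All of this limits the size. It does not settle the rule, because SAP 4.2 and 6.1 handle a run-in longer than 28 days by keeping every diary day and prorating. A programmer could reasonably do the same after dosing. The 4-week window itself is stated correctly for on-time doses.

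**Conclusion.** The point holds as a drafting correction that is worth making before the first lock. The seventh dose and the month 7 dosing day conflict with the six-dose schedule and must be reconciled with it. The visit 5 end should be explicit in 4.4, subject to the check against the source PDF. The late-dose gap comes from the rule as written: 31 to 42 days for a 4-week window and 89 to 98 days for the 12-week window. The figure of 126 days is only an outer bound.

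The size is modest. In the illustration, a routine delay moves an individual value by about 0.2 days (4-week) or 0.1 days (12-week). An emergency delay moves it by about 0.7 or 0.3 days. These figures assume that the migraine rate in the extra days differs by 2 per 28 from the rate in the window. The documents do not say how often visits run late or whether delays differ by arm, so no effect on the treatment difference can be stated.

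**What to change.** Check SAP 4.4 against the source PDF. Then, before the first lock:

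- Define the double-blind window as the 1st dose to the earlier of day 84 and the day before the 4th dose (visit 5).
- Keep months anchored to the actual dose, because Protocol 9.5.2 separates monthly data by dosing visit. End each month at the earlier of 28 days, counted from and including that dosing day, and the day before the next dose, whether that dose is late or missed.
- Define the open-label window as the 4th dose to visit 8 or end of treatment, capped at 84 days.
- Replace the seventh dose and the month 7 dosing day with the visit 8 boundary, set to the previous dose plus 28 days if visit 8 is missed.

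The cost is a few sentences, and a few diary days beyond the caps in patients with delayed visits. With dose-anchored months, a late visit 4 can carry month 3 a little past day 84 (at +3, days 60 to 87), so the monthly and 12-week values may not use identical days. The SAP should say that this is accepted.

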5. STUDY POPULATION

5.1. General

The ITT analysis set will be used for all study population summaries unless otherwise specified. Summaries will be presented by migraine classification (ie, CM, EM, and all), treatment group, all fremanezumab and for all patients. Study population data will also be listed.

For continuous variables, descriptive statistics (n, mean, SD, SE, median, minimum, and maximum) will be provided. For categorical variables, patient counts and percentages will be provided. Categories for missing data will be presented if necessary.

5.2. Patient Disposition

Data from patients screened; patients screened but not randomized and reason for not being randomized will be summarized only for the overall group using patient counts.

Patients randomized (ie. ITT analysis set); patients randomized but not treated; patients in the double-blind mITT, double-blind safety, and PP analysis sets; reasons for exclusion from the PP analysis set, patients who complete the double-blind IMP; and patients who discontinue the double-blind IMP (including reason for discontinuation) will be summarized using descriptive statistics. Data from patients who discontinue the double-blind IMP will also be summarized by reason for withdrawal using descriptive statistics. Patients in the open-label mITT and the open-label safety analysis sets, reason for discontinuation from open-label treatment, reason for discontinuation from the study and patients who complete the study will also be summarized. The denominator for calculating the percentages will be the number of patients in the ITT analysis set.

